### 1.0 Objectives / Specific Aims

We hypothesize that participants receiving the ACB-iPACK intervention will have lower subjective pain scores and lower total opioid consumption in the initial 72-hours of the postoperative window and increased range of motion at subsequent follow up visits with their surgeon.

### 2.0 Background

Adequate analgesia with maintained functionality is crucial to recovery for patients undergoing outpatient anterior cruciate ligament (ACL) reconstruction. Perioperative peripheral nerve blocks have been utilized in these procedures to maximize postoperative pain control, minimize side effects from IV analgesics, and facilitate discharge from PACU. Past research has pointed to adductor canal blocks (ACBs) being superior to femoral nerve blocks (FNBs) for preserving motor strength during postoperative analgesia following knee arthroplasty [1]. Similar studies specifically looking at ACL reconstruction have shown similar analgesic effects between both blocks, with ACBs having a much higher maximal voluntary contraction of the quadriceps while in the PACU [2]. Further studies have found that for patients who underwent TKAs, ACBs were insufficient in reliving posterior knee pain due to the saphenous nerve innervating only the anterior and medial knee [3] [4]. This study looks to determine whether an increasingly used technique called iPACK block can be used to augment postoperative analgesia when used in conjunction with an ACB for ACL reconstruction. iPACK (infiltration between the popliteal artery and the capsule of the posterior knee) is thought to work by blocking branches of the popliteal plexus and genicular nerves, providing analgesia for the posterior knee that ACBs do not cover [5]. Previous studies have shown positive outcomes for TKA patients using an ACB-iPACK combination with regards to subjective pain measures and opioid consumption, however this relationship has not been confirmed for ACL reconstruction [6].

# 3.0 Intervention to be studied (if applicable)

This study will consist of participants 12 years and older undergoing ACL reconstruction using a quadriceps or bone-patella tendon bone (BTB) graft. The primary goal will be to determine the differences in postoperative pain during the first 72 hours when comparing an ACB + iPACK block to an ACB alone. Secondary outcomes will include opioid utilization during the first 72 hours postoperatively and range of motion including terminal knee extension at postoperative follow-up visits.

# 4.0 Study Endpoints (if applicable)

- The primary endpoint will measure subjective pain scores as 12-hour intervals during the first 72 hours of the postoperative window as collected by a study team member.
- The secondary endpoints will measure total postoperative opioid consumption through postoperative day 2, as well as measure the range of motion and terminal knee extension of participants at postoperative follow-up visits.

# 5.0 Inclusion and Exclusion Criteria/ Study Population

Participants being scheduled for an ACL reconstruction procedure who meet inclusion criteria will be approached and offered enrollment upon arriving to the pre-operative area before the procedure.

#### **Inclusion Criteria**

- Age 12 years and older
- Patients who are scheduled to undergo an ACL reconstruction with quadriceps or BTB graft.

#### **Exclusion Criteria**

- Any contraindication to receiving regional anesthesia. This may include infection at the site of injection, allergy to local anesthetic, or pre-existing nerve injury.
- Patients undergoing hamstring graft or allograft for ACL
- Pre-existing infection at the site of injury
- Patients on chronic opioid treatments
- Pre-existing sensory or motor deficit in operative extremity
- Patients having a revision of previous ACL reconstruction
- Pregnant and/or lactating women
- Weighs less than 40kg

## 6.0 Number of Subjects

We will enroll and randomize 82 subjects.

### 7.0 Setting

Participants will be approached about the study during their pre-surgical consultation with their surgeon and formal consent will be obtained while they are in pre-op/holding prior to the procedure, both of which will take place at MUSC's Charleston West campus, or MUSC's Rutledge Tower. The study procedure will also take place at either of these locations.

#### 8.0 Recruitment Methods

The study team will refer to the OR and clinic schedules available on EPIC to see which patients qualify. If time allows, the surgeon will introduce the study during the surgical consultation in clinic and provide an informational brochure about the study. If not, the study will be introduced to the patient in the pre-operative holding area prior to the procedure.

#### 9.0 Consent Process

Consent will be obtained by IRB approved study team members who have a medical degree and are qualified to discuss the clinical nature of the options being offered.

• Potential study participants will be invited to participate in the study. Initial contact will be made with the patient on the day of the scheduled procedure by an IRB

- approved study team member. The study will be explained, and the patient will be given time to read the consent thoroughly and ask any questions. This will happen in the private pre-op area.
- Written informed consent will be obtained if the participant agrees to participate
  after the study is thoroughly explained. For participants under 18 years of age,
  informed consent will be obtained by their parent or legal guardian and assent will
  be obtained from the participants themselves. A copy of the signed informed
  consent will be provided to the participant.

## 10.0 Study Design / Methods

This study will be a prospective, single-center, single-blind randomized controlled trial. Participants will be randomized by using a stratified randomization technique, stratified by sex into two groups:

- 1) continuous adductor canal block alone (ACB Only) or
- 2) continuous adductor canal block with iPACK block (ACB + iPACK).

Preoperative: Adult participants and pediatric patients >70kg will receive 1g Tylenol and 1-2mg midazolam and up to 20mcg of dexmedetomidine for preprocedure anxiolysis. Patients between 12 and 18 years old will receive Tylenol with a dose based on weight (Table 1), and 1-2mg midazolam and up to 20mcg of dexmedetomidine.

Table 1. Tylenol Dosage Based on Weight for Pediatrics		
Weight	Dosage	
≥70kg	1,000mg	
45-70kg	650mg	
<45kg	500mg	

All participants will receive the continuous adductor canal block which consists of 20cc of 0.25% plain ropivacaine and will be given followed by placement of an OnQ pump infusing 0.2% ropivacaine at 6cc/hr. (4cc/hr. for participants less than 60Kg).

Those who are randomized to the ABC + iPACK group will receive an additional block consisting of 20cc of 0.25% Ropivacaine placed in the popliteal fossa between the popliteal artery and the posterior aspect of the capsule of the knee joint.

Participants randomized to the ACB-only group will receive a skin wheal at the same site where the iPACK block would have been placed in an effort to maintain the blind.

Perioperative: Participants will be appropriately sedated as per clinical care.

Postoperative: Participants will be given 0.2mg hydromorphone every 8 minutes as needed for pain, and 5mg of oxycodone may be administered adjunctively as needed if pan scores remain elevated after intravenous hydromorphone

Post-discharge: Participants will be instructed to schedule two post-operative follow up appointments with their surgeon as well as physical therapy. They will also be prescribed the following medication regimen after discharge:

#### Ages 12-18 and <70kg

- Tylenol 650mg q8h
- Naproxen 250mg q8h
- Oxycodone 5mg q4h PRN pain
- Aspirin 81mg daily for DVT prophylaxis

### All patients ≥ 18 years of age and pediatric patients ≥70kg

- Tylenol 1,000mg q8h
- Naproxen 500mg twice daily
- Oxycodone 5-10mg q4h PRN pain
- Aspirin 325mg daily for DVT prophylaxis

Additionally, participants will be instructed to follow the following bracing and weight bearing instructions:

- Weight bearing as tolerated and no brace for isolated ACL reconstruction, small 2 or less sutures and all inside repair
- Brace for bucketed meniscus with inside out repair, and associated mcl, OR large repaid (more than 3 sutures) 0-90, and weight bearing as tolerated in extension
- Non-weight bearing with brace for meniscus roots, and lateral meniscus tears.

Currently, there is no consensus guidelines for venous thromboembolism prophylaxis in the setting of anterior cruciate ligament reconstruction surgery. Moreover, there is no universally agreed-upon dose for use of aspirin in the postoperative state for VTE prophylaxis. There is current evidence which would suggest aspirin is an effective and safe medication for DVT prophylaxis and other major lower extremity orthopedic surgical procedures. Additionally, current practice patterns would suggest that aspirin is the most commonly utilized VTE prophylaxis following anterior cruciate ligament reconstruction. [8]

#### **Baseline and Randomization**

After consenting and confirmation of meeting eligibility criteria, the participant will undergo the procedure as scheduled and as standard of care. The participant will be

randomized before they are anesthetized, as the block will be prepared and placed prior to the start of surgery.

If randomized to ACB-Only (Group A) the participant will receive the ACB block first. The injection site is prepared with a sterile solution, an injection of lidocaine is given to numb the area, then using ultrasound guidance a needle is inserted into the adductor canal at the mid-thigh where a catheter is placed to administer the long-acting anesthetic. Next, to maintain the blind, the participant will receive a skin wheal with lidocaine at the same location as Group B has the iPACK block placed.

Table 5. Post-Op Follow Up Assessments			
Outcome Measure	Instrument	Collected	
Pain Rating	Average pain, most pain, least pain from 0-10 POD Days 0-3		
Opioid Consumption	Number of pills taken in time period POD Days 0-3		
Physical Therapy	Range of Motion and terminal knee extension	Postoperative Visit 1 and 2	
Adverse Events	Adverse Events	Throughout enrollment	

If randomized to ACB + iPACK (Group B) the participant will be administered the ACB first as stated above and the iPACK block second. The iPACK block will be placed at the posterior part of the knee. The area will be numbed first using lidocaine, then using ultrasound guidance, a needle will be inserted in the popliteal fossa between the popliteal artery and the capsule of the knee.

Table 4. Baseline and Intraoperative Assessments		
Demographics		
Baseline		
Pre-op meds including opioids in past 24 hours		
Randomization		
Anesthesia intra-op data		
Surgical techniques		
Adverse Events		

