- Secondary outcomes include cumulative post-operative opiate consumption over time (POD 0 pm, 1 am/pm, and 2 am), and difference in range of motion between surgical and non-surgical leg at first clinic visit (7-21 days post-op) and 6 weeks PO. Associations between these secondary outcomes with block type will be evaluated using a linear mixed approach. Similar to the primary outcome, models will include fixed effects for type, time, and the interaction between block type and time. The model for cumulative opiate consumption will also include a fixed effect for intra-operative opiates received and the model for range of motion will include a fixed effect for pre-operative difference in range of motion between surgical and non-surgical leg.
- All data will be kept on a password protected MUSC server and in a REDCap database. All paper data sheets will be kept in a locked cabinet, in a locked office that only IRB approved study team members have access to. Participants will be given a study ID number that will be used to identify them throughout the study.

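### The opioid endpoint has no dose unit, Table 5's pill count cannot register intravenous hydromorphone and conflicts with the survey's dose fields, and the analysis window stops short of the 72-hour hypothesis

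*Combined protocol and SAP*

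**What the plan says.** **Measure.** Table 5 (Section 10.0, Baseline and Randomization) records opioid consumption as "Number of pills taken in time period", collected on POD 0-3. The Follow-Up text describes something richer: the text survey asks which pain medicines were taken, with their dose and frequency, and for participants still admitted the medicines come from the chart. Sections 4.0 and 11.0 speak of total or cumulative consumption and give no unit.

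**Opioids given.** Before discharge, Section 10.0 states: "Participants will be given 0.2mg hydromorphone every 8 minutes as needed for pain, and 5mg of oxycodone may be administered adjunctively as needed". The condition for the oxycodone is that pain "scores remain elevated after intravenous hydromorphone", so the hydromorphone is intravenous and comes first. After discharge, adults and heavier paediatric patients have "Oxycodone 5-10mg q4h PRN pain"; the lighter paediatric group has 5 mg per dose.

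**Window.** The hypothesis in Section 1.0 is "lower total opioid consumption in the initial 72-hours of the postoperative window", and Section 3.0 also says 72 hours. Section 4.0 says "total postoperative opioid consumption through postoperative day 2". Table 6 collects to noon of POD 3. The Section 11.0 model uses "cumulative post-operative opiate consumption over time (POD 0 pm, 1 am/pm, and 2 am".

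**Covariates.** The Section 11.0 opioid model adjusts for opiates given during surgery. It does not mention those given in recovery.

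**The concern.** Opioid consumption is named in the trial's hypothesis, yet the only measure stated for it is a count of tablets. The first opioid offered after surgery is not a tablet. If Table 5 is followed literally, that drug is missing from the outcome, and the model does not bring it back as a covariate. If the Follow-Up text is followed instead, doses are available, but nothing says how to add intravenous hydromorphone to oral oxycodone. Two analysts could build different endpoints from the same data, and the choice could be made after the data have been seen.

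The window adds a second open choice. A result accumulated to POD 2 am does not test a 72-hour hypothesis, although data for the remaining period will have been collected.

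**Working it through.** The plan states no effect size, standard deviation or power for opioid consumption, so there is no figure of its own to reproduce. The check compares the sections and adds simple arithmetic.

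**1. What a pill count registers.** Each postoperative hydromorphone dose is 0.2 mg intravenously. Five doses give 5 × 0.2 = 1.0 mg and count as 0 pills, the same as no opioid.

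For scale only, assume that 1 mg intravenous hydromorphone equals 15-20 mg oral morphine and that 1 mg oral oxycodone equals 1.5 mg oral morphine. Neither factor is in the documents. Then:

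- 4 doses: 0.8 mg, or 12-16 mg oral morphine. Dividing by 1.5 gives 8.0-10.7 mg oxycodone, or 1.6-2.1 tablets of 5 mg.
- 5 doses: 1.0 mg, or 15-20 mg oral morphine. This is 10.0-13.3 mg oxycodone, or 2.0-2.7 tablets.
- 8 doses (about one hour at 8-minute intervals): 1.6 mg, or 24-32 mg oral morphine. This is 16.0-21.3 mg oxycodone, or 3.2-4.3 tablets.

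The dose counts are illustrations. The plan gives no expected recovery-room dose.

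**2. Whether another section captures the intravenous dose.**

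- Table 6 has a POD 0 period from waking to discharge, so a collection period covering recovery exists. The instrument that Table 5 assigns to POD 0 is the pill count.
- The text messages start the next morning, and the first of their periods begins at discharge.
- Chart abstraction is stated for participants who are admitted, in a sentence about the text-message follow-up. Section 2.0 describes the surgery as outpatient.
- The item that the Follow-Up text explicitly records before leaving the PACU is the pain score.

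For a participant discharged the same day, the intravenous dose is therefore neither clearly in the outcome nor in the model as a covariate.

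**3. The windows on one clock.** The last column is hours before the end of Table 6 (noon of POD 3).

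| Place | Window | End point | Hours short |
|---|---|---|---|
| Sections 1.0 and 3.0 | first 72 hours | about noon POD 3 | about 0 |
| Table 5 | POD 0-3 | hour not given | - |
| Table 6 | waking to noon POD 3 | noon POD 3 | 0 |
| Section 4.0 | through POD 2 | midnight closing POD 2 | 12 |
| Section 11.0, if 2 am means up to noon of POD 2 | POD 0 pm to POD 2 am | noon POD 2 | 24 |
| Section 11.0, if 2 am means Table 6's POD 2-AM row | same | midnight closing POD 1 | 12 + 12 + 12 = 36 |

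The last row arises because the Table 6 message labelled POD 2-AM asks about noon to midnight of the day before. The 24-hour reading has more support, because the pain paragraph of Section 11.0 describes its POD 2 point as before noon.

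In hours since surgery, let surgery end at hour *h* on POD 0, with *h* assumed between 10 and 16:

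- midnight closing POD 1: 48 − *h* = 32-38 h
- noon POD 2: 60 − *h* = 44-50 h
- midnight closing POD 2: 72 − *h* = 56-62 h
- noon POD 3: 84 − *h* = 68-74 h

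Only the full Table 6 schedule comes close to 72 hours.

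**The case against.** The best defence is that one cell of Table 5 is not the endpoint definition. Sections 4.0 and 11.0 do not adopt a pill count, the Follow-Up text collects dose, and Table 6 covers the recovery period. This stands in part. A reader might infer that the plan commits to scoring intravenous hydromorphone as zero and so misstates consumption. The documents do not go that far: they leave the unit undefined and contain two instruments that disagree. The defence does not supply a unit, a conversion rule or explicit chart capture for same-day discharges.

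Three further inferences are tempting and should not be drawn:

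- **That tablet strength is ignored.** The survey asks for dose, and nothing says that tablets of different strengths are dispensed. At 6 doses a day the regimens allow 6 × 5 = 30 mg or 6 × 10 = 60 mg, but if all tablets are 5 mg a count is proportional to milligrams (6 or 12 tablets).
- **That no opioid saving in recovery could show.** Oxycodone is also allowed before discharge and could be counted if given as a tablet. Only the intravenous part is at risk.
- **That the planning study places the opioid effect in the first 8 hours.** Section 11.0 cites that study for a pain-score difference against a different comparator. It reports nothing there on opioid use.

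It is also fair to say that the POD 2 cut-off is not peculiar to opioids, since Section 11.0 applies it to pain as well, and that the choice between 72 hours and POD 2 belongs to the sponsor. Neither point removes the need to reconcile the sections.

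**Conclusion.** The concern holds as a gap in definition. The opioid endpoint has no unit and no rule for combining intravenous and oral drug. Table 5 and the Follow-Up text disagree on the instrument. Capture of intravenous opioid is not explicit for participants discharged the same day.

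The modelled window falls about 24 hours short of what is collected if POD 2 am runs to noon, or about 36 hours on Table 6's label. That is 24/72, or one third, and 36/72, or one half, of the hypothesised period.

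The size and direction of any bias in the treatment comparison cannot be computed, because the documents give no expected opioid use in either arm. The tablet equivalents above rest on assumed conversion factors and dose counts; they show only that the uncounted amount need not be negligible. The endpoint is secondary but forms part of the stated hypothesis, so it should be settled before analysis.

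**What to change.** 1. In Table 5, replace the pill count with total opioid dose in oral morphine milligram equivalents, and name one conversion table in the plan before any data are examined. Use the same unit in Sections 4.0 and 11.0.
2. State that intravenous and oral opioids given between waking and discharge are taken from the chart for every participant, including those who go home the same day, and that post-discharge opioids come from the survey's dose fields.
3. Reconcile the window across Sections 1.0, 3.0, 4.0 and 11.0 and Tables 5 and 6. If the 72-hour hypothesis is kept, accumulate over all Table 6 periods. Identify each modelled time point by the hours it covers, because the row labels name when the message is sent.

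The cost is revised wording, a conversion step and a short chart abstraction for all participants. The survey already collects post-discharge dose. Treatment does not change.

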#### Follow-Up

The participant will be asked to provide their average pain score, worst pain score, and lowest pain score using a visual analog scale from 0-100 with 100 being the worst at various time points during the postoperative period. The first pain scores will be recorded before they leave the PACU on the day of the procedure. Beginning the following morning, the participant will receive a text message link sent by Twilio's secure server that opens a survey housed in RedCap. The first text message will arrive at 9:00 AM and will follow the schedule in Table 6.

They will receive a text message from a secure server asking the average pain questions as well as what medications they took for pain (including medication name, dosage, and frequency). The set of questions will state what time window (example:

12:00 AM midnight the night prior to 12:00 PM noon the same day) to consider when answering the questions. If the participant has been discharged from the hospital, they will answer these questions in the text message each day. If they are admitted to the hospital at this point in time, the information will be gathered from their chart for medications and asked verbally for pain scores. Range of motion and terminal knee extension will also be recorded at the in-person postoperative follow up visits.

If the participant is unable or unwilling to receive text messages, they will be provided a document to record their pain and medications for the pre-determined intervals so when a study member contacts them, they are able to relay their answers back accurately.

Table 6. Post-Op Follow Up Assessment Schedule			
Post-Op Day	Time of Text Message	Data Collection Time Period	
POD 0	Right before discharge	Waking up from surgery to discharge	
POD 1-AM	9:00 AM	Discharge to 11:59 midnight prior	
POD 1-PM	3:00 PM	12:00 AM midnight night prior to 12:00 PM noon same day	
POD 2-AM	9:00 AM	12:01 PM noon day prior to 11:59 AM midnight night prior	
POD 2-PM	3:00 PM	12:00 AM midnight prior to 12:00 PM noon same day	
POD 3-AM	9:00 AM	12:01 PM noon day prior to 11:59 AM midnight night prior	
POD 3-PM	3:00 PM	12:00 AM midnight prior to 12:00 PM noon same day	

### 11.0 Data Management

- The study will be a double-blinded randomized controlled trial of participants undergoing ACL reconstruction at one academic medical center. Although the anesthesiologist administering the block will not be blinded, the surgeons, participants, and study statistician will be blinded to treatment assignment. Participants will be randomized to receive either ACB or ACB + iPACK block. We will use stratified randomization, stratifying on biologic sex, to ensure similar distributions of male/female participants in each treatment arm the same.
- The primary outcomes of interest are participant reported postoperative pain over time and quadricep strength based on the leg raise and knee extension test. Postoperative VAS pain score reported as average, worst, and least pain will be collected on post-op day 0 (after 12pm), 1 (prior to 12 pm and after 12 pm), and 2 (before 12 pm). The association between postoperative pain with block type will be evaluated using a series of linear mixed models evaluating average pain, worst pain, and least pain as dependent variables. Models will include fixed effects for preoperative pain score, block type, postoperative time, and the interaction between block type and post-operative time and a random subject effect to account for correlation between pain scores collected on the same subject over time. Model assumptions will be checked graphically, and transformations will be considered as needed. The difference in patient reported pain between block type by post-operative time and pain score type will be evaluated using a series of linear contrasts. A similar study

by Amer  $(2018)^1$  comparing combined Adductor Canal and iPACK Blocks versus combined Adductor Canal and Periarticular Injection blocks for pain management in ACL Reconstruction Surgery found a difference in VAS pain scores of 1.5 between 0 to 8 hours post-op and standard deviation in VAS pain of 2.5 units. A sample size of n=35 participants per treatment arm (70 total) with at least 3 measures of pain provides 80% power to detect a difference in pain score of 2 units at significance level  $\alpha=0.004$  (Bonferroni corrected for 4 comparisons) and assuming a compound symmetric covariance structure with a conservative standard deviation = 3.0 and correlation within subject is  $\rho=0.33$ . We will enroll 41 participants (82 total) in each arm to allow for up to 20% attrition.

- Secondary outcomes include cumulative post-operative opiate consumption over time (POD 0 pm, 1 am/pm, and 2 am), and difference in range of motion between surgical and non-surgical leg at first clinic visit (7-21 days post-op) and 6 weeks PO. Associations between these secondary outcomes with block type will be evaluated using a linear mixed approach. Similar to the primary outcome, models will include fixed effects for type, time, and the interaction between block type and time. The model for cumulative opiate consumption will also include a fixed effect for intra-operative opiates received and the model for range of motion will include a fixed effect for pre-operative difference in range of motion between surgical and non-surgical leg.
- All data will be kept on a password protected MUSC server and in a REDCap database. All paper data sheets will be kept in a locked cabinet, in a locked office that only IRB approved study team members have access to. Participants will be given a study ID number that will be used to identify them throughout the study.

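### Section 11's pain time list stops at noon of POD 2 although the primary endpoint runs 72 hours; its alpha does not fit its own label; and it names a strength primary outcome that is never scheduled

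*Combined protocol and SAP*

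**What the plan says.** **The endpoint.** Section 1 hypothesises "lower subjective pain scores and lower total opioid consumption in the initial 72-hours of the postoperative window". Section 3 gives the primary goal as to "determine the differences in postoperative pain during the first 72 hours". Section 4 is the most specific: "The primary endpoint will measure subjective pain scores as 12-hour intervals during the first 72 hours of the postoperative window". In Sections 3 and 4 pain is the only primary item.

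**Collection.** Table 5 schedules pain on POD 0 to 3. Table 6 has seven rows. The first covers "Waking up from surgery to discharge" and the second "Discharge to 11:59 midnight prior". The other five are half-days, the last ending at noon of POD 3. Each morning survey asks about the previous day. The POD 2-AM and POD 3-AM rows, for example, cover "12:01 PM noon day prior to 11:59 AM midnight night prior".

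**Analysis.** Section 11 has three pain scores (average, worst, least), which it says "will be collected on post-op day 0 (after 12pm), 1 (prior to 12 pm and after 12 pm), and 2 (before 12 pm". Three mixed models, one per score, have "fixed effects for preoperative pain score, block type, postoperative time, and the interaction between block type and post-operative time". Block differences are then tested by contrasts at each time and for each score. The sample size uses alpha 0.004, described as Bonferroni for four comparisons, with 35 per arm, at least three measures, a difference of 2, SD 3.0 and correlation 0.33.

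**Second primary outcome.** Section 11 adds quadriceps strength, by leg raise and knee extension test, to the primary outcomes. Tables 4, 5 and 6 schedule no such test. Table 5 does schedule terminal knee extension, but together with range of motion, and Section 4 makes both secondary.

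**The concern.** The endpoint sections and the analysis section describe different primary analyses. An analyst who follows Section 11 literally would test four times and leave the last part of the 72 hours untested. An analyst who follows Section 4 would test six or seven windows at an alpha that was apparently sized for four. The plan does not say which prevails, so the primary windows and the alpha could be chosen after the data are seen. A block effect confined to the early hours and one that lasts 72 hours would support different conclusions, so the choice could change the trial's main result. The strength outcome is a further gap: taken literally, one named primary outcome cannot be reported, because nothing in the schedule measures it.

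**Working it through.** **1. Windows.** Table 6 rows by data period, set against Section 11's four times:

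| Table 6 row | Data period | Listed, by clock time | Listed, by survey label |
|---|---|---|---|
| POD 0 | Waking to discharge | Unclear | Yes |
| POD 1-AM | Discharge to midnight | Yes | Yes |
| POD 1-PM | Midnight to noon, POD 1 | Yes | Yes |
| POD 2-AM | Noon to midnight, POD 1 | Yes | Yes |
| POD 2-PM | Midnight to noon, POD 2 | Yes | No |
| POD 3-AM | Noon to midnight, POD 2 | No | No |
| POD 3-PM | Midnight to noon, POD 3 | No | No |

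By clock time the omitted span is noon POD 2 to noon POD 3: 24 h, 2 of 7 rows. By survey label it is midnight at the start of POD 2 to noon POD 3: 36 h, 3 of 7 rows. Neither figure depends on the hour of surgery.

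**2. The plan's sample size.** Inputs from Section 11: difference 2, SD 3.0, rho 0.33, m = 3 measures, alpha 0.004. Sidedness is not stated. I assume two-sided, which reproduces the plan's n; one-sided gives 31 per arm.

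- Effective SD of a participant's mean = 3.0 × sqrt((1 + 2 × 0.33)/3) = 2.232.
- n per arm = 2 × (2.878 + 0.842)² × 2.232² / 2² = 34.5, rounded up to 35. This reproduces the plan.
- SE of the difference at 35 per arm = sqrt(2 × 9 × (1 + (m − 1) × 0.33)/m/35) = 0.533 for m = 3. Power is 80.8% by normal approximation (77.5% by noncentral t, 68 df).

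The stated 35 is therefore the sample size for a *time-averaged* difference over three measures.

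**3. Alpha.** 0.05/4 = 0.0125, so the label does not produce 0.004. 0.05/12 = 0.0042, which rounds to 0.004 and fits 4 times × 3 scores. That origin is an inference; the plan does not state it.

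| Contrasts | Bonferroni bound if 0.004 is kept | Matching alpha |
|---|---|---|
| 4 times × 3 scores = 12 | 0.048 | 0.0042 |
| 6 windows × 3 scores = 18 | 0.072 | 0.0028 |
| 7 windows × 3 scores = 21 | 0.084 | 0.0024 |
| 6 windows × 1 score = 6 | 0.024 | 0.0083 |
| 7 windows × 1 score = 7 | 0.028 | 0.0071 |

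Six is 72/12, from Section 4. Seven is the number of Table 6 rows.

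**4. Power at 35 per arm** (normal approximation, same SE formula; m = 1 gives SE 0.717):

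| Alpha | Single window (m = 1) | Average, m = 3 | Average over all windows |
|---|---|---|---|
| 0.004 | 46.4% | 80.8% | not applicable |
| 0.05/18 | 42.0% | 77.6% | 88.6% (m = 6) |
| 0.05/21 | 40.2% | 76.1% | 89.2% (m = 7) |
| 0.05/6 | 56.0% | 86.7% | 94.0% (m = 6) |
| 0.05/7 | 53.9% | 85.5% | 94.3% (m = 7) |

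The Bonferroni family consists of single-window contrasts, so the m = 1 column is the one that belongs with it.

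**5. Strength.** Section 11 and its secondary-outcome paragraph give models for pain, opioid use and range of motion only. The power statement and alpha are for pain. Nothing covers strength.

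**The case against.** The strongest reply is that nothing is lost. Every Table 6 survey is scheduled, and the model's general term for postoperative time could take in the later windows. Both statements are correct, and they are why the repair needs only wording. They do not settle the matter, because the conclusions rest on contrasts at named times, and the later windows are not among those named.

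A reader might infer that 0.004 can serve only the four listed times. The documents do not support that without a condition. The twelve-contrast origin is inferred, and with one primary score 0.004 would cover all seven windows (bound 0.028). The excess over 0.05 arises only if all three scores are tested in every window. Section 11's contrasts point that way, but it does not say whether all three scores are primary.

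A reader might also infer that covering 72 hours makes the trial too small, since 80.8% falls to about 76%. That comparison sets alpha by seven windows but averages only three measures, and Section 11 gives three as a minimum. With all windows in the average, power is 88.6% or 89.2%. For single-window contrasts power is low, but it is already about 46% under the present plan, so the added windows are not the main cause.

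Finally, seven windows is not the only reading. Section 4's wording gives six 12-hour intervals, and the two POD 0 rows of Table 6 are not fixed 12-hour periods. This stands, and the fix leaves both counts open.

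**Conclusion.** The point holds and should be corrected before unblinding. Section 11's time list does not cover the 72-hour primary endpoint: 24 or 36 hours of scheduled pain data fall outside it, depending on how the list is read. The mismatch between alpha and its label is plain arithmetic. The bound of 0.072 or 0.084 is conditional on 0.004 being kept while all three scores are tested in six or seven windows. The strength outcome has no scheduled measurement, model, power or alpha, and it conflicts with Section 4, where pain is the only primary endpoint.

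The power figures assume two-sided tests, compound symmetry and the plan's own SD and correlation. They do not show that the 72-hour analysis needs a larger sample. The fault is that the primary analysis is not fixed in advance.

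Two other mismatches are separate items to reconcile and carry no weight here. Opioid use runs over 72 hours (Sections 1 and 3), through POD 2 (Section 4) or to the morning of POD 2 (Section 11). Pain is scored 0 to 10 in Table 5 and 0 to 100 under Follow-Up.

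**What to change.** In Section 11:

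- List the primary pain windows by data period, not survey label, so that they cover the 72-hour endpoint through noon of POD 3. Say whether the PACU row and the discharge-to-midnight row, which varies in length, count as primary windows.
- Correct the comparison count and alpha to match. With three scores, use 0.05/18 = 0.0028 for six windows or 0.05/21 = 0.0024 for seven. Alternatively, name one primary score before unblinding and use 0.05/6 = 0.0083 or 0.05/7 = 0.0071, with the other two scores secondary.
- Restate power at 35 per arm by what is tested. With three scores and six or seven windows, the time-averaged difference has 77.6% or 76.1% with the three-measure minimum, and 88.6% or 89.2% with all windows. A single-window contrast has about 42% or 40%, against 46% now.
- Remove quadriceps strength from the primary outcomes, to agree with Sections 3 and 4 and Table 5.

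The cost is wording only, with no new data collection. The downside is a somewhat stricter alpha if three scores are kept, or two scores becoming secondary if one is named.
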